
Reference product, dose and route of administration:
 
1. Prednefrin® SF. Prednisolone Acetate 1%. Prepared by Allergan, S.A. of C.V.
 
- Dosage: 1 drop 4 times a day (every 4 hours) during the period of vigil in the operated eye, for 14 days. Dose reduction for 14 days at the discretion of the principal investigator.- Route of administration: topical ophthalmic

Evaluation criteria:
 
Effectiveness:
 
 • Primary 
 o Cellularity in the anterior chamber • Secondary 
 o Visual capacity (CV) o Central thickness of the retina or Clinical corneal edema or conjunctival hyperemia or Flare o Symptomatology 
 - Pain - Photophobia 
Tolerability:
 
 • Post-Stretching Ocular Symptomatology 
Security:
 
 • Visual capacity (CV) • Adverse events (EA) • Intraocular pressure (PIO)

Statistical methodology:
 
The result of the continuous quantitative variables will be presented in measures of central tendency: mean, standard deviation and ranges. The total size of the samples will consider an eye as a case for the evaluation of efficacy.
 
The normal distribution of the results will be obtained through the Kolmogorov-Smirnov and Shapiro-Wilks test. The statistical analysis of the continuous quantitative variables to find significant differences (p) will be in the inter-group analysis: t test for paired samples; for intra-group analysis: McNemar test. Evaluations of cellularity in the anterior chamber before the application of the intervention and in the final visit will be considered for the analysis. The level of difference to consider significance will be an alpha of 0.05 or less. The result of nominal and ordinal qualitative variables will be presented in frequencies, proportions and percentages. The statistical analysis to identify significant differences of the qualitative variables will be done creating 2x2 contingency tables and will be carried out as follows: Difference between groups: χ^2 test (Chi-square) of Pearson or Fisher's exact in expected values less than 5 ; for intra-group analysis: McNemar test

Page left intentionally blank

2. Content

1. SUMMARY	1
2. CONTENT	5
3. ABBREVIATION INDEX	9
4. ADMINISTRATIVE STRUCTURE OF THE STUDY	11
5. INTRODUCTION	13
5.1 THEORETICAL FRAMEWORK	13

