The development of postoperative inflammation is variable from case to case, depending on factors such as the use of drugs prior to surgery, the hardness of the lens, the technique used and the presence of concomitant diseases. [24] [25] Several studies have demonstrated the correlation between the increase in the degree of NO and NC of the LOCS III classification and the increase in the power of phacoemulsification and the effective time of ultrasound in cataract surgery, together with the increase in post-surgical inflammation. [26] [27] [9]

There are no established treatment guidelines to prevent or reduce inflammation after eye surgery. [28] [19] Therefore, the treatment includes pre and postoperative anti-inflammatory therapy with corticosteroids and / or nonsteroidal anti-inflammatory drugs (NSAIDs) see Table 2. Anti-inflammatories. Because it is impossible to predict which patients will develop clinically significant inflammation, post-surgical use of anti-inflammatory drugs is routinely performed, with corticosteroids being the most commonly used. [28] [29]

[figure not shown]

Figure 1. Cascade of inflammation

Table 2. Anti-inflammatories

Group	Mechanism of action	Effect	Effectiveness	Security
Corticosteroids	Inhibition of phospholipase A2	It decreases the production of prostacyclins, thromboxane A2, prostaglandins and leukotrienes. Alters the inflammatory mediators of transcription. Modulates the activity and migration of inflammatory cells.	Decreases the presence of inflammatory cells. And the postoperative pain.	Its adverse effects include: cataracts, ocular hypertension, glaucoma, decreased scarring
NSAIDs	Alters transcription and translation.	Suppression of prostaglandin production	Similar to corticosteroids. They have shown better results in decreasing the breakdown of the blood-gas barrier.	Decreased corneal sensitivity.

Corticosteroids are traditionally used to control eye inflammation in the short term and are the most used therapeutic option after cataract surgery. Compared with NSAIDs, corticosteroids have a greater range of activity in the control of inflammation, by acting at multiple points in the inflammation cascade, including both the cyclooxygenase (COX) and phospholipase A2 pathways, reducing prostaglandins. and leukotrienes. See Figure 1. [19]

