5.2 Definition of the problem and fundamental reason

The inflammation after ocular surgery continues to be an undesirable consequence despite multiple advances in technology and surgical techniques. Control and prevent inflammation is of great interest to the surgeon in his eagerness to achieve optimal results.

Although it is true that currently cataract surgery does not necessarily result in significant inflammation, there is still a portion of patients who will experience some type of postoperative inflammation, which could potentially alter the visual result, not to mention the comfort of the patient.

Because it is impossible to determine who these patients will be, most surgeons use prophylactic regimens of anti-inflammatory drugs, because of their wide range of action, corticosteroids are the cornerstone of these regimens.

Difluprednate, the active ingredient of PRO-145, is a potent synthetic difluorinated corticosteroid derived from prednisolone, which in its ophthalmic formulation comes in the form of an emulsion. This gives it the advantage over other corticosteroids that are usually formulated as suspension, since it avoids flocculation, sedimentation and poor redispersibility, all of which can lead to dosing errors during administration.

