6.2 Eligibility criteria.

6.2.1 Inclusion criteria.

- Signed informed consent.
- Age ≥ 18 years.
- Both sexes.
- Postoperative cataract surgery by phacoemulsification.
 - o That they have met the criteria for phacoemulsification and a classification of the LOCS III cataract of NO ≥ 2 and NC ≥ 2 .

6.2.2 Exclusion criteria.

6.2.2.1 General criteria.

- Pregnant women, lactating or planning to get pregnant.
- Women of reproductive age and who do not have a hormonal contraceptive method, intrauterine device or bilateral tubal obstruction.
- Participation in another clinical research study ≤ 30 days before the baseline visit.
- Have previously participated in this same study with the contralateral eye.
- That they can not comply with their attendance at appointments or with all the requirements of the protocol.

6.2.2.2 Medical and therapeutic criteria.

- Surgery in both eyes in the same surgical shift.
 - Time > 24 hours after having surgery.
 - LIO placement outside the bag.
 - Presentation of rupture of the posterior capsule, with or without the presence of vitreous.
 - Carrying out an iridectomy, or lesion of the pupillary sphincter during phacoemulsification surgery.
 - Scheduled for surgical intervention in the contralateral eye during the study period.
 - History of glaucoma or ocular hypertension.
 - History of increased PIO with the use of steroids.
 - PIO ≥ 24 .
 - History of uveitis.
 - Presence of corneal abrasion or corneal ulceration in the study eye.
 - Use of steroids or topical NSAIDs, 24 hours prior to surgery and until the start of instillation of investigational drugs.
 - Use of anticoagulants, systemic steroids or immunomodulators in the last two weeks
 - Periocular injection of any steroid in the study eye 4 weeks before the start of the instillation of the investigational drugs.
 - Use of storage steroids 2 months prior to the start of instillation of investigational drugs.
 - Presence or suspicion of keratitis and / or viral, bacterial or fungal conjunctivitis.
 - Presence or suspicion of endophthalmitis.
 - Presence or suspicion of toxic syndrome of the anterior segment.
 - Severe corneal edema that does not allow assessment of the anterior chamber
 - Macular diseases.
-
- Diabetes Mellitus with A1C $\geq 6.5\%$ (48 mmol / mol) or fasting glucose (no caloric intake by ≥ 8 hours) of ≥ 126 mg / dL (7.0 mmol / L).
 - Any disease or condition that requires the use of topical or systemic NSAIDs during the time of intervention.

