In the presence of intraocular inflammation, the increased permeability of the non-pigmented layer of the ciliary epithelium, the posterior epithelium of the iris and the vascular endothelium of the iris results in the accumulation of cells and proteins (visible to the examiner as flare) in the anterior chamber. Using a light beam of 0.2mm X 0.2mm directed obliquely to the anterior chamber with a forward inclination of the light source (slit lamp tower) the degree of flare and cellularity will be determined according to the group of work of standardization for the nomenclature of uveitis. [70] The degree of agreement to the granted rating will be reported in the CRF. (See Table 6 and Table 7)

Table 6. Scale for anterior chamber cellularity.

Grade	Number of cells
0	Any

½ +	1-5
1 +	6-15
2 +	16-25
3 +	26-60
4 +	More than 60

Visible in a field of 0.2mm x 0.2mm

Table 7. Flare scale

Grade	Number of cells
0	There is no flare
1 +	Mild
2 +	Moderate (iris and crystalline clearly visible)
3 +	Marking (iris and crsitalino slightly blurred)
4 +	More than 60 (fibrin)

6.4.3.2 Visual ability.

Visual acuity (AV) is a test of visual function. Spatial visual acuity is the ability to distinguish separate elements of an object and identify them as a whole. It is quantified as the minimum separation angle (located at the nodal point of the eye) between two objects that allows perceiving them as separate objects.

Snellen's notation is described as the distance at which the test is performed, divided by the distance at which the letter is vertically equivalent to 5 arc minutes. Thus, at 6 meters a letter 6/6 (20/20) equals 5 minutes of arc, a letter 6/12 (20/40) equals 10 minutes, and a letter 6/60 (20/200) equals 50 minutes. The Snellen fraction can also be expressed as a decimal (ie 20/20 = 1 and 20/40 = 0.5). [71]

The AV will be evaluated basally, without refractive correction with the Snellen chart. Which will be located in a place with adequate lighting, natural or artificial and at a distance of 3m from the subject to be evaluated. The visual acuity of each eye will be taken, starting with a right eye (OD) asking the subject to keep both eyes open and using an occluder to cover the left eye (OS); the subject will read aloud the lines that the evaluator points out, the line of smaller letters that he reaches to see will be annotated by the fractional evaluator as the AV of the OD in the clinical record. Proceed to the OS with the same method.

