By means of optical coherence tomography (OCT) the GCR will be measured; Because this is a multicenter study it is not feasible to standardize the brand and model of the OCT to be used, it will allow the use of OCT Stratus (Carl Zeiss), Cirrus (Carl Zeiss), Spectralis (Heidelberg Engineering) with the minimum requirement that the baseline and final OCT are performed with the same OCT, with the same protocol and these characteristics are recorded in the clinical note and in the CRF, together with the central average.

6.4.3.6 Tonometry.

Tonometry is the objective measure of PIO, based primarily on the force required to flatten the cornea, or the degree of corneal indentation produced by a fixed force. Goldman's tonometry is based on the Imbert-Fick principle. [71]

The tonometry will be carried out, after instillation of the topical anesthetic, with fluorescein and the use of the cobalt blue filter (after the evaluation of the surface staining). There will be 2 shots and the average will be calculated, which will be recorded in the clinical file. The average will be registered in the CRF.

6.4.4 Measurement time.

- Measurements at the baseline visit

- Biomicroscopy
- Visual ability
- History of symptomatology
- OCT
- Tonometry
- Evaluation of adverse events
- Measurements in visit 1 and 2
- Biomicroscopy
- Visual ability
- Evaluation of adverse events
- History of symptomatology
- Tonometry
- Measurements in final visit
- Biomicroscopy
- Visual ability
- Adverse event evaluation
- History of symptomatology
- OCT
- Tonometry
- Measurements on security call
- Evaluation of adverse events

6.5 Schedule and study diagram.

The **baseline visit** will be considered on day 1 of the study and should be within the first 24 postoperative hours, the IP will indicate the subject to start the application of the investigational products that same day. If necessary, adjust the scheme so that it complies with the 4 applications of day 1; however, in the event that during the opening hours it is not feasible to adjust the 4 applications, the IP will indicate the application of at least 2 instillations, with a minimum of 2 hours between them.

Visit 1 will be performed in relation to the start of treatment on day 7 with a window period of ± 2 days.

The **visit 2 and final** will be made on days 14 and 29, respectively, with a window period of ± 2 days for visit 2 and + 3 days for the final.

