8.3 Statistical methodology

8.3.1 Analysis of primary and secondary outcome variables

The statistical analysis will be carried out by personnel of Sophia Laboratories. The statistical program SPSS version 19 will be used.

The designated personnel will be blinded to the intervention groups. The coding will be done using consecutive numbers for each intervention group.

The data will be collected and sorted in an excel sheet. Later they will be exported to the platform of the SPSS program. The variables will be categorized according to their nature.

The results of the continuous quantitative variables will be presented in measures of central tendency: mean, standard deviation and ranges. See **Table 5 Variable measurement method**. The total size of the samples will consider an eye as a case for the evaluation of the efficacy.

The normal distribution of results will be obtained through the Kolmogorov-Smirnov and Shapiro-Wilks test, as applicable.

The statistical analysis of the continuous quantitative variables to find significant differences (p) will be the following:

. Inter-group analysis: t test for paired samples.

. Intra-group analysis: Mc Nemar test. Cellularity assessments in the anterior chamber will be considered for the analysis before the application of the intervention and in the final visit. The level of difference to consider significance will be of an alpha of 0.05 or less.

The result of nominal and ordinal qualitative variables will be presented in frequencies, proportions and percentages. See **Table 5 Method for measuring variables**

The statistical analysis to identify significant differences of the qualitative variables will be done by creating 2x2 contingency tables and will be done as follows:

- Difference between groups: χ^2 test (Chi-square) of Pearson or Fisher's exact in expected values less than 5.
- Intra-group analysis: Mc Nemar test.

The level of difference to consider significance will be an alpha of 0.05 or less.

For the reporting of adverse events all eyes of those participants who were randomly assigned to an intervention group will be considered. The results will be expressed in number of cases.

The final report of the results will be shown in tables or graphs, as appropriate.

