8.3.3 Population analysis and management of missing data

The effectiveness analysis will consider those cases in which the measurements of the baseline and final visit are met. Those subjects who do not comply with any of these measurements will not be integrated into the final database to evaluate the effectiveness. Nevertheless, an intention to treat analysis (ITT) will be carried out.

The safety assessment will include in the analysis all those subjects (considering one eye or both) who have been exposed at least once to any of the interventions regardless of the visit in which they were eliminated from the study.

9. Methods Monitoring

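### The between-arm test of anterior-chamber cells leaves out the recorded baseline grade; stratifying by it is an optional, low-cost efficiency gain, nil in power at the protocol's own rates

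*Combined protocol and SAP*

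**What the plan says.** Section 5.5.2 sets the specific objective as elimination of anterior-chamber cells at the final visit. Table 5 (section 6.4.3) classes cellularity as ordinal. For nominal and ordinal variables, section 8.3.1 says the analysis "will be done by creating 2x2 contingency tables and will be done as follows", and names Pearson's chi-square, or Fisher's exact test for small expected counts, between groups and McNemar within groups. The statistical methodology in the Summary says the same ("will be done creating 2x2 contingency tables and will be carried out as follows"). Neither place names a covariate or stratum for the between-group test, or the cut that makes the 2x2 table.

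The baseline grade is available. Biomicroscopy is scheduled at baseline (6.4.4, 6.5.1), and section 6.4.3.1 says of the cell and flare grades: "The degree of agreement to the granted rating will be reported in the CRF". Section 8.3.3 limits the effectiveness analysis to "those cases in which the measurements of the baseline and final visit are met". Section 8.3.1 mentions pre-treatment cellularity only beside the within-group item.

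Section 6.2 sets no minimum cell grade for entry. Section 7.1 balances allocation within centre, not by cell grade.

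**The concern.** Baseline grade plausibly predicts whether an eye is clear four weeks later. An eye that starts at grade 0 has nothing to eliminate, yet counts as a success if it is clear at the end. A comparison that ignores baseline mixes such eyes with those that can show a treatment effect. If a share f of eyes start at grade 0 and finish with the same rate in both arms, the between-arm difference shrinks by the factor (1 - f).

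Two things are at stake. One is some power, if a real difference exists. The other is interpretation: the trial compares two active steroids, and similar arms are easier to read if it is known how the drugs compare in eyes that had cells to clear. The within-arm McNemar table, if cut at cells present or absent, would show how many eyes per arm started with cells, but no between-arm comparison in those eyes is planned.

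**Working it through.** **The plan's own figure.** Section 6.6.1 gives 78.9% v 77.5%, z values 1.96 and 0.84, and 74 per group. The two-proportion formula gives n = (1.96 + 0.84)² × (0.789×0.211 + 0.775×0.225) / 0.014² = 7.84 × 0.3409 / 0.000196 ≈ 13,634 per group. So 74 does not follow from these rates. The inflation does reproduce: 148 × 1.2 = 177.6, rounded to 178. At 74 or 89 per arm, two-sided power at the stated rates is about 5.5%, and stays at 5 to 6% for f from 0 to 20%.

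**A working effect.** To see what stratifying could do, a larger difference must be assumed. I used 78.9% v 58.0% clearance in eyes with cells. The 58.0% has no source; it was chosen because 7.84 × (0.1665 + 0.2436) / 0.209² = 73.6, so 74 per arm gives 80% power. The 78.9% in section 6.6.1 is a rate for reduction of cell grade, and is used here only as an assumed clearance rate.

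**Dilution, elimination reading.** If grade-0 eyes stay clear, each arm's rate is f + (1 - f)p. At f = 10% this is 0.810 v 0.622: difference 0.188, unpooled SE at 74 per arm 0.0725, power Φ(0.188/0.0725 - 1.96) ≈ 74%.

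| Share at grade 0 | 0% | 5% | 10% | 20% |
|---|---|---|---|---|
| Power, 74 per arm | 80% | 77% | 74% | 66% |
| Power, 89 per arm | 87% | 84% | 81% | 74% |

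**Dilution, reduction reading.** If response means a lower grade (6.6.1), grade-0 eyes cannot respond and each rate is (1 - f)p. At 74 per arm:
- f = 10%: 0.710 v 0.522, SE 0.0784, power about 67%.
- f = 20%: 0.631 v 0.464, SE 0.0807, power about 54.5%.

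**Gain from a stratified test.** Simulation under the elimination reading, 20,000 trials per cell, 74 per arm. The assumed mix of grades ½+, 1+, 2+ and 3+ or above is 25/35/25/15%. The strata are grade 0; ½+ and 1+; 2+ and above. The slope is the assumed fall in log-odds of clearance per grade step. Entries are CMH power minus chi-square power, in points.

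| Slope | f = 0% | 5% | 10% | 20% |
|---|---|---|---|---|
| 0 | -0.6 | +0.2 | +0.9 | +3.3 |
| 0.3 | +0.1 | +0.7 | +1.6 | +4.0 |
| 0.6 | +1.8 | +2.4 | +3.6 | +5.6 |
| 1.0 | +4.8 | +6.2 | +6.9 | +9.5 |

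Gains at 89 per arm are within 1 point of these. Type I error was 4.6 to 5.3% for CMH and 4.5 to 5.3% for chi-square. If 10 to 20% of grade-0 eyes later have cells, the gain at slope 0.6 is +1.8 to +2.1 points (f = 10%) and +1.8 to +3.3 (f = 20%). A different set of assumptions (93% v 77.5%, another grade mix, grades not pooled, f up to 30%) gave about -1.5 to +7 points.

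**At the protocol's rates.** With 78.9% v 77.5% the change in power is at most about 0.3 points, which is simulation noise. Precision changes slightly. If grade-0 eyes stay clear and the other eyes share one rate p', the variance ratio is p/p'. With p = 0.775, p' = (0.775 - f)/(1 - f), so the ratio is 0.775/0.750 = 1.033 at f = 10% and 0.775/0.719 = 1.078 at f = 20%. The 95% interval narrows by 1 - 1/√1.033 = 1.6% and 1 - 1/√1.078 = 3.7%. The unadjusted width is 2 × 1.96 × √(0.3409/74) = 26.6 points, so the saving is about 0.4 and 1.0 points.

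**Centre.** Stratifying by centre alone changes power by -0.1 to +1.1 points (3 or 6 centres assumed). Crossing centre with all five grades gives -4.6 to +4.6.

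**The case against.** The strongest case is that this is a preference. The unadjusted test is standard, there is no power gain at the rates the protocol assumes, and every non-zero gain needs a treatment effect, a grade mix, a slope and a grade-0 share that the documents do not give. That stands, and it limits the point to an optional improvement.

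It is also fair that the hypothesis in section 5.5.4 is not worded as a between-arm claim, and that the McNemar test uses baseline. But 8.3.1 does plan a between-group test and 5.6.1 states a comparative aim; McNemar compares no arms.

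A reader might infer several stronger things that the documents do not support:
- *That the unadjusted test is wrong.* Randomisation protects its type I error. That the chi-square or Fisher test applies at all rests on Table 5: the cellularity sentence in 8.3.1 sits in the continuous-variable block, whose inter-group test is a paired t test.
- *That many eyes will enter at grade 0.* The documents point both ways. Section 5.2 says "there is still a portion of patients who will experience some type of postoperative inflammation" and 5.1 says "The development of postoperative inflammation is variable from case to case". Against that, 5.1 says cataract surgery induces inflammation, the baseline visit "should be within the first 24 postoperative hours" (section 6.5), the LOCS III criterion selects denser cataracts, and section 6.2.2.2 excludes "Use of steroids or topical NSAIDs, 24 hours prior to surgery and until the start of instillation of investigational drugs". The share may be low.
- *That restricting to eyes with cells keeps the randomised comparison whatever the analysis set.* The restriction is pre-treatment, but the efficacy set is already selected after randomisation by final-visit completion (8.3.3) and adherence (6.3.2).

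**Conclusion.** The point holds as one of efficiency, not error. If cellularity is handled as ordinal, the planned between-arm test leaves out a baseline value that is already collected. Under an assumed 78.9% v 58.0%, 74 per arm, 0 to 20% of eyes at grade 0 and slopes from 0 to 1.0, pooled-grade stratification changes power by about -0.6 to +9.5 points. If few eyes start at grade 0 and the slope is modest, the change is near the low end. At 78.9% v 77.5% there is no power gain, only a slightly narrower interval and a clearer reading of similar arms. Confidence is medium because the documents give neither the grade distribution nor its link with clearance. The sample-size calculation is a separate and larger problem that this does not touch.

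**What to change.** In section 8.3.1 and the Summary:

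1. State that the between-arm comparison of response, defined as cell grade 0 at the final visit (5.5.2), is a CMH test with a Mantel-Haenszel risk difference and 95% confidence interval, stratified by baseline cell grade.
2. Keep grade 0 as its own stratum and pool the other grades by a rule fixed before unblinding, for example ½+ with 1+, and 2+ and above.
3. Keep the unadjusted chi-square or Fisher test as a sensitivity analysis. Add centre only under a stated pooling rule that avoids sparse cells; centre alone is not a remedy.
4. Add a supporting between-arm analysis in eyes with baseline grade above 0, run in the intention-to-treat set of 8.3.3. Its value is mainly interpretive: at f = 10% and 74 per arm, power under the working effect is 76% against 74% for all eyes.

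No new data, visits or patients are needed. The costs are a protocol amendment, which section 10.2 sends through committee review and regulatory authorisation, and a loss of up to about 0.6 power points if grade is not prognostic and no grade-0 eyes enter.

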5.5 Objectives and hypothesis

5.5.1 General purpose

To evaluate the efficacy of the ophthalmic emulsion PRO-145 in the treatment of inflammation and pain after phacoemulsification.

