6.3.4.2 Storage

The medication must be stored in a secure area with restricted access. Storage should be at room temperature to no more than 30 ° Celsius.

The research center has the obligation to record, in the format designated by the sponsor, the temperature and humidity registered in the data logger. This record should include the current temperature and humidity, as well as the minimum and maximum of each of these. It must be done at least once a day, on business days.

Said data will be compared by the clinical monitor according to the registration in the data logger.

6.3.4.3 Return.

The research subjects will return, to the personnel indicated by the IP in the center, their treatments in the final visit.

The refund will be made by the research center when the sponsor indicates it. Prior to the return the research center must make a count of the assigned medication and the remaining medication, with the aim of creating an inventory which serves for the final filling of the medication return form.

6.4 Outcome variables.

6.4.1 Security variables.

6.4.1.1 Primary outcome variables.

Visual ability

Adverse events

Intraocular pressure.

6.4.1.2 Tolerability variables.

Symptomatology postinstillation

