6.4.2.2 Secondary outcome variables

Visual ability

Central thickness of the retina

Clinical corneal edema

Conjunctival hyperemia

Flare

Ocular symptomatology (pain and photophobia)

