6.5.3 Diagram of the study

[figure not shown]

Figure 4. Diagram of the study

6.6 Sample size.

The sample size calculated for the present study is 178 subjects.

Divided into two intervention groups, each group will be comprised of 89 subjects. Each subject will provide an eye for efficacy analysis.

6.6.1 Calculation of the sample size.

The sample size was calculated using the formula for two proportions variables as well as the data was entered into the online calculator, software developed in: www.powerandsamplesize.com based on Chow S et al. [72]

With a statistical confidence of 95% corresponding to the type I error, equal to 1.96, with a power of 80%, corresponding to the type II error, equal to 0.84. A 78.9% efficiency ratio was considered in the reduction of the degree of cells in the anterior chamber after the application of 4 weeks of difluprednate 0.05% in 79 subjects submitted to phacoemulsification compared to an efficiency ratio of 77.5% with the use of 1% prednisolone. [53]

According to the previous calculation, the result is 74 eyes per group. The total when considering 2 intervention groups is 148 eyes, which was increased by 20% (30 eyes) for the probable losses. The total sample size required is 178 eyes. **Total n = 178 eyes.**

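### Each of 7 to about 28 secondary efficacy comparisons is called significant at 0.05 with no testing order, and pain has no rank, named score, visit or valid test

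*Combined protocol and SAP*

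**What the plan says.** Section 8.3.1 is headed as covering both primary and secondary outcomes. For continuous variables it lists a between-group t test, written as a paired test, and ends: "The level of difference to consider significance will be of an alpha of 0.05 or less". For nominal and ordinal variables it lists a chi-square or Fisher test on 2x2 tables and ends: "The level of difference to consider significance will be an alpha of 0.05 or less". No section ranks the secondary variables, names a key secondary, or adjusts for the number of tests.

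The general objective in 5.5.1 concerns efficacy "in the treatment of inflammation and pain after phacoemulsification", and the title also names pain. The hypothesis (5.5.4), the primary efficacy variable (6.4.2.1) and the sample size (6.6.1) rest on anterior chamber cells alone. Pain appears only in the last line of an unranked list in 6.4.2.2: "Ocular symptomatology (pain and photophobia)".

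Section 6.4.3.4 records each symptom as a severity score and a frequency score, both 0 to 4. Table 5 types symptomatology as discrete; 8.3.1 gives tests only for continuous variables and for nominal or ordinal ones.

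**The concern.** With a single threshold and no order, any secondary score that reaches p<=0.05 may be reported as a significant difference between PRO-145 and prednisolone. The reader of the final report could not tell a planned finding from the best of many.

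Pain is the sharpest case because the title and general objective invite a claim on it. The plan does not say whether severity or frequency counts, or at which visit. The choice of visit matters: 6.4.3.4 asks about symptoms since the last visit, so the recall period is about 6 days at visit 1 (day 1 to day 7) and about 15 days at the final visit (day 14 to day 29). Nor is there a usable test. The discrete type has none assigned, a paired t test does not fit two independent groups, and a 2x2 table needs a cut-point on the 0 to 4 score that the plan does not give.

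**Working it through.** The plan states neither a number of comparisons nor a family-wise error rate, so there is no figure of its own to reproduce on this point. Both are derived here.

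**Step 1: count the between-arm secondary efficacy comparisons.**

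Inputs:
- Variables: 6.4.2.2 lists visual capacity, retinal thickness, corneal edema, hyperemia, flare, pain and photophobia. Section 5.5.3 adds cells on the ordinal scale.
- Scores: two per symptom (6.4.3.4).
- Visits: three after baseline (6.4.4 and 6.5.1), except retinal thickness, which is measured after baseline only at the final visit.

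Section 8.3.1 does not say which visits or scores are tested for the secondary variables, so several readings are possible:
- Final visit only, variables of 6.4.2.2, one score per symptom: 7.
- Final visit only, adding ordinal cells and both scores per symptom: 10.
- Three visits, variables of 6.4.2.2, one score per symptom: 6 x 3 + 1 = 19.
- The same with ordinal cells: 7 x 3 + 1 = 22.
- The same with both scores per symptom: 9 x 3 + 1 = 28.

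**Step 2: chance of at least one false positive among k tests.**

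Assume no true difference anywhere and two-sided tests at 0.05, which is 0.025 in the direction favouring PRO-145.
- Independent tests, either direction: 1 - 0.95^k. For k = 7 this is 0.302; for k = 28 it is 0.762.
- Independent tests, favouring PRO-145: 1 - 0.975^k. For k = 7 this is 0.162; for k = 28 it is 0.508.
- Correlated tests: normal test statistics with one common correlation of 0.5. This value is an assumption; the documents give none. The probability was obtained by numerical integration over the shared component.

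| k | Either direction, independent | Either direction, correlation 0.5 | Favouring PRO-145, independent | Favouring PRO-145, correlation 0.5 |
|---|---|---|---|---|
| 7 | 30.2% | 23.0% | 16.2% | 11.5% |
| 10 | 40.1% | 28.7% | 22.4% | 14.4% |
| 19 | 62.3% | 40.9% | 38.2% | 20.5% |
| 22 | 67.7% | 43.9% | 42.7% | 22.1% |
| 28 | 76.2% | 49.1% | 50.8% | 24.7% |

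At k = 28 the expected number of false positives is 28 x 0.05 = 1.4, of which 0.7 favour PRO-145.

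**Step 3: what a gate on the primary would cost pain.**

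The sample size in 6.6.1 is stated as follows: "With a statistical confidence of 95% corresponding to the type I error, equal to 1.96, with a power of 80%". It assumes 78.9% on difluprednate ("A 78.9% efficiency ratio was considered in the reduction of the degree of cells in the anterior chamber"), "compared to an efficiency ratio of 77.5% with the use of 1% prednisolone", and reports 74 eyes per group.
- Standard error of the difference at 74 per group: sqrt[(0.789 x 0.211 + 0.775 x 0.225)/74] = 0.0679.
- Expected z: 0.014/0.0679 = 0.206.
- Chance of significance favouring PRO-145: Phi(0.206 - 1.96) = about 4%. Adding the opposite direction, Phi(-0.206 - 1.96) = about 1.5%, gives about 5.5%.
- For comparison, 80% power on these rates needs (1.96 + 0.84)^2 x 0.3409/0.014^2 = about 13,600 eyes per group.

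The sample size is a separate issue. It matters here because a superiority gate on these rates would almost never open.

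**The case against.** The strongest reply is that the plan has one primary efficacy variable, one hypothesis and a sample size built on cells alone. The primary type I error is therefore untouched. The secondary objectives in 5.5.3 are worded arm by arm, and none states a superiority claim. Both remarks are correct and limit the point to secondary claims. They do not remove it, because 8.3.1 still prescribes between-group tests and attaches the word significant to each result at 0.05.

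The reply also holds against three stronger readings that a reader might infer:
- **That 28 tests are planned.** They are not. Only ordinal cells has an objective that refers to successive visits (5.5.3). Section 8.3.1 names baseline and final visit for cells, and 8.3.3 defines the efficacy set by those two visits. Section 8.3.2 describes the between-visit work as internal and does not say that it compares arms. Separate tests of severity and frequency are also an inference from how they are recorded. The figure of 28 is the top of a range.
- **That a chance advantage for PRO-145 is likely.** The 76% counts both directions and assumes independence, which is implausible for repeated scores on the same eye. The chance in PRO-145's favour reaches 51% only for 28 independent tests; it is 25% at correlation 0.5 and 16% for 7 independent tests.
- **That the safety variables headed as primary in 6.4.1.1 add to the problem.** They sit under the separate security heading, and the summary lists only cells as primary for efficacy. This is a matter of labelling, not multiplicity.

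**Conclusion.** The concern holds for the secondary claims. Following the stated rule gives a 30% to 76% chance of at least one false difference if the tests are independent, or about 23% to 49% at an assumed correlation of 0.5. For a false advantage of PRO-145 the ranges are 16% to 51% and about 11% to 25%. That is a material risk, but not a probable outcome on most readings. Even the lowest either-direction figure, 23%, is more than four times the nominal 5%.

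These figures rest on the absence of any true difference, on the reconstructed range of 7 to 28 comparisons, and on a correlation that the documents do not supply. The finding on pain needs none of these assumptions: it is prominent in the title and general objective, yet lacks a rank, a named score, a visit and a valid test. The point deserves correction before unblinding but does not threaten the primary analysis.

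**What to change.** Amend 8.3.1 as follows:
1. Define the primary between-arm cell comparison as superiority, or as non-inferiority with a stated margin. Settle this together with the sample-size correction.
2. Name one pain endpoint as the single key secondary, for example pain severity (0 to 4) at one visit chosen before unblinding. Compare arms on the ordinal score, allowing for baseline severity, with a proportional-odds model or a stratified Wilcoxon test. Test it at 0.05 only if the primary comparison succeeds.
3. Report all other secondary variables, visits and frequency scores as estimates with 95% confidence intervals and no significance claim.

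The fixed order keeps the error rate for the two claims together at 0.05 without reducing the alpha of the primary. Bonferroni over 28 tests would instead require 0.05/28 = 0.0018 for each.

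Costs: other secondary p-values can no longer be called significant. Pain can be claimed only if the primary succeeds, which would be rare if the gate is superiority at the plan's stated rates (about 4% in PRO-145's favour at 74 per group). Because 8.3.1 is part of the protocol, the change must pass through the amendment procedure in 10.2, including committee review and regulatory authorization. No extra patients or measurements are needed for this change itself.
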